10.0 PHARMACOLOGY PLAN

Not applicable.

11.0 DATA COLLECTION AND MONITORING AND ADVERSE EVENT REPORTING

11.1 Records to Be Kept

CRFs will be provided for each participant. Participants must not be identified by name on any CRFs. Participants will be identified by the patient identification number (PID) and study identification number (SID) provided by the ACTG DMC upon randomization/participant registration.

11.2 Role of Data Management

11.2.1 Instructions concerning the recording of study data on CRFs will be provided by the ACTG DMC. Each CRS is responsible for keying the data in a timely fashion.

11.2.2 It is the responsibility of the ACTG DMC to assure the quality of computerized data for each ACTG study. This role extends from protocol development to generation of the final study databases.

11.3 Clinical Site Monitoring and Record Availability

11.3.1 Site monitors under contract to the U.S. NIAID will visit participating CRSs to review the individual participant records, including consent forms, CRFs, supporting data, laboratory specimen records, and medical records (physicians' progress notes, nurses' notes, individuals' hospital charts), to ensure protection of study participants, compliance with the protocol, and accuracy and completeness of records. The monitors also will inspect sites' regulatory files to ensure that regulatory requirements are being followed and sites' pharmacies to review product storage and management.

11.3.2 The site investigator will make study documents (e.g., consent forms, drug distribution forms, CRFs) and pertinent hospital or clinic records readily available for inspection by the local IRB/EC, the site monitors, the U.S. NIAID, or the U.S. OHRP for confirmation of the study data.

11.4 Expedited Adverse Event (EAE) Reporting to DAIDS

11.4.1 Adverse Event Reporting to DAIDS

Requirements, definitions, and methods for expedited reporting of AEs are outlined in Version 2.0 of the DAIDS Expedited Adverse Event (EAE) Manual, which is available on the RSC website at <http://rsc.tech-res.com/safetyandpharmacovigilance/>.

The DAIDS Adverse Experience Reporting System (DAERS), an internet-based reporting system, must be used for expedited AE reporting to DAIDS. In the event of system outages or technical difficulties, expedited AEs may be submitted via the DAIDS EAE Form. For questions about DAERS, please contact DAIDS-ES at [contact]. Site queries may also be sent from within the DAERS application itself.

Sites where DAERS has not been implemented will submit expedited AEs by documenting the information on the current DAIDS EAE Form. This form is available on the RSC website: <http://rsc.tech-res.com/safetyandpharmacovigilance/>. For questions about EAE reporting, please contact the RSC ([contact]).

11.4.2 Reporting Requirements for this Study

- The suspected, unexpected serious adverse reaction (SUSAR) Reporting Category, as defined in Version 2.0 of the DAIDS EAE Manual, will be used for this study.
- There are no study agents for this protocol. All Grade 3 and 4 SAEs that are related to study procedures should be reported.
- In addition to the SUSAR Reporting Category identified above, other AEs that must be reported in an expedited manner are cervical, vaginal, and vulvar cancers and miscarriages.

11.4.3 Grading Severity of Events

The DAIDS AE Grading Table, Version 1.0, December 2004 (Clarification August 2009) and Addendum 1-Female Genital Grading Table for Use in Microbicide Studies are used and available on the RSC website at <http://rsc.tech-res.com/safetyandpharmacovigilance/>.

11.4.4 Expedited AE Reporting Period

- The expedited AE reporting period for this study is as per the EAE manual.
- After the protocol-defined AE reporting period, unless otherwise noted, SUSARs, as defined in Version 2.0 of the EAE Manual, will be reported to DAIDS if the study staff become aware of the events on a passive basis (from publicly available information).

12.0 HUMAN PARTICIPANTS

12.1 IRB/EC Review and Informed Consent

This protocol and the informed consent document (Appendix I) and any subsequent modifications will be reviewed and approved by the IRB/EC responsible for oversight of the study. A signed consent form will be obtained from the participant or legal guardian/representative. The consent form will describe the purpose of the study, the procedures to be followed, and the risks and benefits of participation. A copy of the consent form will be given to the participant or legal guardian/representative and this fact will be documented in the participant's record.

12.2 Participant Confidentiality

All laboratory specimens, evaluation forms, reports, and other records that leave the site will be identified by coded number only to maintain participant confidentiality. All records will be kept locked. All computer entry and networking programs will be done with coded numbers only. Clinical information will not be released without written permission of the participant, except as necessary for monitoring by ACTG, IRB/EC, the U.S. NIAID, the U.S. OHRP, or any host country regulatory entities.

12.3 Study Discontinuation

The study may be discontinued at any time by the ACTG, IRB/EC, the U.S. NIAID, the U.S. OHRP, or other government agencies as part of their duties to ensure that research participants are protected.

13.0 PUBLICATION OF RESEARCH FINDINGS

Publication of the results of this trial will be governed by ACTG policies.

14.0 BIOHAZARD CONTAINMENT

As the transmission of HIV and other blood-borne pathogens can occur through contact with contaminated needles, blood, and blood products, appropriate blood and secretion precautions will be employed by all personnel in the drawing of blood and shipping and handling of all specimens for this study, as currently recommended by the Centers for Disease Control and Prevention and the U.S. NIH.

All dangerous goods materials, including diagnostic specimens and infectious substances, must be transported using packaging mandated by CFR 42 Part 72. Please refer to instructions detailed in the International Air Transport Association (IATA) Dangerous Goods Regulations.

## 1 Introduction

This document describes the proposed content for the primary statistical analysis report for ACTG study A5282. The plan includes the key analyses that will form the core of presentation or publication used to disseminate the primary conclusions of the study. It is recognized that this statistical analysis plan (SAP) may be modified by the Study Team as new information becomes available or to reflect recommendations made by the Data Safety Monitoring Board (DSMB).

## 2 Study Overview

### 2.1 Study Design

A5282 is a randomized clinical trial designed to compare a human papillomavirus (HPV) test-and-treat strategy with a cytology-based strategy for the prevention of CIN2+ (cervical intraepithelial neoplasia [CIN] grade 2 [CIN2], 3 [CIN3], or invasive cancer). The study has two components:

- (1) a randomized open-label comparison between immediate cryotherapy (test-and-treat strategy; Arm A) and cytology-based strategy (Arm B) in participants detected with high-risk HPV (hr-HPV), and
- (2) a brief cohort follow-up for participants for whom cryotherapy is inappropriate (Arm C).

The study is a proof-of-concept study to evaluate if a “test-and-treat” strategy is promising in HIV-infected women in resource limited settings.

All participants are screened with the Abbott RealTime hr-HPV test (aHPV) to detect hr-HPV infection. [This test semi-quantitatively detects the presence of type 16, type 18, or the presence of any of the other 12 types of hr-HPV (31, 33, 35, 39, 45, 51, 52, 56, 58, 59, 66, and 68).]

At screening, the examiner also performs a visual inspection and colposcopy without biopsies to determine whether the candidate’s cervix is suitable for cryotherapy. Candidates suitable for cervical cryotherapy have:

- (i) no visible cervical lesions, or
- (ii) any visible lesions are located entirely on the ectocervix and are no more than 2 to 3 mm into the endocervical canal, and visible lesions cover less than 75% of the cervix, and all visible lesions are deemed appropriate for cryotherapy by the treating health care provider.

[figure not shown]
Participants with cervical lesions inappropriate for cryotherapy are not eligible for randomization (Arms A or B) but are eligible to register to Arm C. Participants without hr-HPV (by aHPV) are also eligible to register to Arm C if lesions were seen on the screening colposcopy or if the screening cytology shows high-grade squamous intraepithelial lesions (HSIL).

Participants in Arm A undergo cervical cryotherapy at entry. Participants in Arm A receive the results of the cytology, but participants receive cryotherapy treatment regardless of the results. Participants in Arm B follow a cytology-based management plan involving three steps – cytology, colposcopy with directed biopsies, and loop electrosurgical excision procedure (LEEP), as needed. Participants in Arms A and B are seen at regular intervals post entry for evaluation using aHPV, HPV DNA PCR, cervical cytology, and cervical colposcopy and directed biopsies for a total follow-up length of 130 weeks.

Participants in Arm C undergo colposcopy and directed biopsies. If CIN2+ is detected by biopsy, then LEEP is performed and a follow-up visit 26 weeks after these procedures is scheduled for evaluation using aHPV, HPV DNA PCR, GeneXpert, cervical cytology, and cervical colposcopy and directed biopsies. After the week 26 visit, Arm C participants go off study.

All participants undergoing cryotherapy or LEEP are seen 4 weeks post-procedure to evaluate potential AEs from the procedure. Quality assurance procedures are in place for reviews of digital impressions rendered during colposcopies (no lesions seen, lesions seen/appropriate for cryotherapy, or lesions seen/not appropriate for cryotherapy). Slides from biopsies with and without CIN2+ are reviewed regionally and possibly centrally. HPV DNA PCR and GeneXpert are performed on stored specimens and results are not used for clinical management.

**Figure 1:** Overview of Study Design

## 2.2 Primary Hypothesis

The primary hypothesis of the study is, in HIV-infected women with hr-HPV, immediate cryotherapy results in a lower probability of CIN2+ than a cytology-based strategy.

## 2.3 Study Objectives

**The primary objective of the study is to evaluate the effectiveness of immediate cryotherapy (Arm A) in HIV-infected women with hr-HPV compared to a cytology-based strategy (Arm B) by comparing cumulative CIN2+ rates from week 26 to week 130.**

The secondary objectives are:

- **To evaluate the safety and tolerability of cervical cryotherapy (Arm A) in HIV-infected women.**
- **To compare between arms the presence of cervical cytological abnormalities during the study.**
- **To assess study discontinuation rates and reasons for discontinuation between arms.**
- **To compare the time to development of CIN2+ between those women with and without detection of hr-HPV by aHPV at 26 weeks, and those women with and without cervical cytological abnormalities after cervical cryotherapy in Arm A.**
- To assess detection frequencies of cervical HPV types (by DNA PCR) and the rates of hr-HPV by GeneXpert at study entry.
- To evaluate baseline/screening characteristics (detection of various HPV types, CD4, CD4 nadir, HIV RNA, sexual history and recent sexual activity) associated with cytological abnormalities at baseline.
- To evaluate the sensitivity and specificity of GeneXpert for hr-HPV detection as measured by aHPV and HPV DNA PCR at study screening and the agreement beyond chance between these measures. [PEPFAR Objective]
- To report the proportion of HIV-infected women with extensive cervical lesions inappropriate for cryotherapy and examine possible factors associated with these lesions including CD4 count, plasma HIV-1 RNA, ART use, HPV types detected, sexual history and recent sexual activity. [PEPFAR Objective]

The tertiary objectives are:

- To compare between arms the presence of hr-HPV by aHPV and HPV DNA PCR during the study.
- To assess the HPV types detected (by DNA PCR) at the time of CIN2+ detection by cervical swab and in histopathology specimens.

**NOTE:** Only the highlighted objectives will be addressed by the current analysis plan. The other objectives were addressed in previous analyses.

### **3 Statistical Considerations**

Unless otherwise indicated, analysis will use data from all subjects who enrolled successfully to A5282 arms A and B.

For categorical measures, number of subjects and percent will be provided. For continuous measures, median, lower and upper quartiles, minimum and maximum will be provided. In data listings, participants will be identified by an anonymous patient identifier generated at the statistical center. Dates will not be shown, but will be converted to time (e.g. weeks) since randomization.

Time to CIN2+ will be computed as the number of weeks between randomization and the week 26 to week 130 biopsy week when CIN2+ was first detected. For those who did not develop CIN2+, event time will be censored at the latest among the following: time of last biopsy or last colposcopy or last pap smear. The cumulative rate of CIN2+ will be estimated using Kaplan-Meier methods. A one-sided 95% upper confidence bound on Arm B minus Arm A cumulative rates accounting for baseline ART use (i.e. [using inverse variance as weights,] weighted estimate of treatment difference across baseline ART use) will be provided.

The per-protocol secondary analysis of the primary endpoint will only include:

- a. Arm A participants who had week 0 cryotherapy, and
- b. Arm B participants with: 1) baseline NILM cytology, 2) baseline abnormal cytology (ASCUS or greater) with one or more cervical biopsies that show NILM or CIN1 as the most severe result, 3) baseline abnormal cytology (ASCUS or greater) who underwent cervical colposcopy with no lesions seen, or 4) women who had LEEP performed prior to week 16 after the week 0 CIN2+ on biopsy regardless of cytology result.

All programs that generate derived data will be validated. The calculations of time to CIN2+ and confidence interval for the primary endpoint (one-sided 95% upper confidence interval for arm B proportion minus arm A proportion) will be double-programmed.

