Part of this study is being funded by a supplement from the U.S. NIH to conduct implementation science research of interest to the President’s Emergency Plan for AIDS Relief (PEPFAR). The PEPFAR objectives in section 1.3 will use screening and baseline evaluations from all women who give consent for this study. The availability of the **xpert hrHPV** ~~careHPV~~ test should broaden access to cervical cancer screening through the HPV test-and-treat strategy. It will be critical to understand how this test performs in HIV-infected women. ~~Although this assay has been conformité européenne (CE) marked, it will not be widely available until late 2011.~~ This study will compare **xpert hrHPV** ~~careHPV~~ results to two other HPV tests: HPV DNA PCR and aHPV. Cryotherapy is not recommended for women with extensive cervical lesions. Data from our Zambian investigators suggest that 15-20% of HIV-infected women will have such lesions and that half of these women will have CIN2/3 or invasive/microinvasive cancer on histology [40, 41]. Algorithms for cervical cancer screening must address treatment of these women to maximally impact mortality from cervical cancer.

2. Per the March 2015 interim DSMB review, biopsies are being added to study follow-up visits for all participants, regardless of preceding colposcopy results.

- Section 3.0, fourth paragraph, now reads: Participants in Arms A and B will be seen at regular intervals post entry for aHPV, HPV DNA PCR, cervical cytology, and cervical colposcopy and directed biopsies for a total follow-up length of 130 weeks. **At least two cervical biopsies should be performed at the week 78 and week 130 visits. Visible lesions should be biopsied preferentially. If no visible lesions are seen, then two random biopsies should be obtained.**
- Section 6.3.10, subsection on colposcopy and directed biopsies, now reads:

Post entry:

- Participants in Arms A and B will undergo colposcopy and directed biopsies at the weeks 26, 78, and 130 clinic visits. **At least two cervical biopsies should be performed at the week 78 and week 130 visits. Visible lesions should be biopsied preferentially. If no visible lesions are seen, then two random biopsies should be obtained.**
- Participants in Arm C who undergo LEEP post-entry will undergo colposcopy

and directed biopsies at the week 26 clinic visit.

Digital images and colposcopic impression will be submitted for review, along with location of cervical biopsies.

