(The following paragraph supersedes Clarification Memo [CM] #2, dated 01/02/1014.) Directed biopsies will be obtained from areas suspicious for CIN. ~~Biopsies are taken only if lesions are seen upon colposcopy.~~ In the event lesions are not seen upon colposcopy but the cytology specimens show presence of HSIL, then the participant should return to the study clinic for repeat colposcopy and other diagnostics procedures such as endocervical curettage (ECC), random cervical biopsies (**if not already done**), or diagnostic LEEP. Results of these diagnostic tests must be recorded on the appropriate CRF. ~~Slides from biopsies of CIN2+ and biopsies without CIN2+ will be submitted for review.~~ If CIN2+ is detected by biopsy, the participant will undergo LEEP.

- c. Sample Informed Consent, What do I have to do if I am in this Study?, Groups A and B: At the study visit about 6, 18, and 30 months after the entry visit you will also have a colposcopy and biopsies if any abnormal areas are seen. **At months 18 and 30, you will have two biopsies performed whether or not abnormal areas are seen.**

3. Additional clarifications were made to Section 6.3.10.

- a. The subsection, "Diagnoses," now reads:

Diagnoses

(Per CM #1, dated 02/05/1013.) After entry, record any new diagnoses made since the last visit using the ACTG criteria for clinical events and other diseases.

(Per CM #1, dated 02/05/1013.) Except for invasive cancer, cervical cytology and histology results do not need to be recorded as events; these results will be entered on study-specific CRFs only.

(New language) Record all histology results from procedures for the diagnosis or treatment of cervical HSIL (such as cervical conization or hysterectomy) and from biopsies performed related to the presence or absence of squamous intraepithelial lesions on the appropriate CRFs.

- b. The subsection, "LEEP," now reads:

(The following paragraph supersedes item 4b in LoA #2, dated 08/09/1012.)

LEEP

Participants found to have CIN2+ by biopsy at any point during the study will be offered LEEP **or other excisional treatment** (except for participants in Arm A **prior to week 26** who have CIN2+ on pre-cryotherapy biopsy at entry). If the participant had a prior LEEP, treatment of recurrent **or incompletely treated**

CIN2+ is at the discretion of the site investigator. These participants will continue on study.

(No changes to the remainder of this subsection.)

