9.4 Sample Size and Accrual

For the primary analysis, cumulative occurrence of CIN2+ on biopsy from week 26 to week 130 will be compared between Arms A and B.

The study reported by Kuhn et al [22] implies about a 43% cumulative rate of CIN2+ among women infected with HIV at entry in the delayed evaluation arm compared to about 7% in the HPV test-and-treat arm (comparable to Arm A) for HIV-infected and hr-HPV positive women with 3-year follow-up. However, unlike the delayed evaluation arm in Kuhn's study, some of the women in Arm B in the current study may be diagnosed with CIN2+ based on the abnormal baseline cervical cytology that leads to colposcopy and possibly successful treatment within 26 weeks. Hence, the CIN2+ rate in Arm B is likely to be less than 43% approximated from the delayed evaluation arm in Kuhn's study. It is approximated that 24% of the hr-HPV-positive, HIV-infected women will be diagnosed with CIN2+ at the first colposcopy, based on the baseline HPV prevalence and the month 6 colposcopy results reported by Kuhn et al [22]. Assuming that the sensitivity of cervical cytology is approximately 80% and the efficacy of the treatment is 90%, it is approximated that 17% of the HPV-infected women in Arm B will be diagnosed with CIN2+ and treated successfully prior to week 26. Taking into account that these CIN2+ events will not count as events in the A5282 study, using an assumed exponential distribution for time to event to adjust for the shorter follow up time in A5282 compared to the Kuhn study, and using the three year cumulative event rates of 7% and 43% in the Kuhn study's HPV-and-treat arm and delayed evaluation arm, respectively, we estimate the cumulative CIN2+ event rate from week 26 to week 130 in Arm A and Arm B to be about 6% and 20%, respectively.

As a proof-of-concept study, the protocol team plans to conduct a one-sided test using time-to-event methods that adjust for interval censored data at a type 1 error rate of 5% to show improvement with immediate cryotherapy (Arm A) with at least 90% power. Assuming a 20% rate in Arm B and 6% rate in Arm A leads to a study sample size of 111 in each arm. Table 2 below presents a conservative estimate [42] of the power to detect various rate differences between the study arms with the sample size of 111 in

each arm using a Fischer's exact test. Based on simulations, the actual analysis method will have at least as much power as presented in Table 2.

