9.6 Analyses

9.6.1 Comparison of CIN2+ between Arms A and B

For the primary analysis, time-to-event methods will be used to estimate the cumulative rate of the primary endpoint (from week 26 to week 130 after study entry) to account for lost to follow-up. The protocol team plans to use the Turnbull estimation for the proportions of participants without CIN2+ diagnosis by the end of the study, stratified by the study stratification factors [43]. The generalized Greenwood's formula for the standard error will be used for the variance and inverse variance method to account for strata [44]. The proportions in Arms A and B will be compared using asymptotic normal distributions. A one-sided 95% upper confidence bound on the difference (Arm B proportion minus Arm A proportion) between these proportions will also be provided. A stratified log-rank test will be conducted as a secondary analysis to compare the time to development of CIN2+ between Arms A and B. The primary analysis will be conducted as intent-to-treat on all participants randomized to the study Arms A and B. In other words, participants will be included in the analyses even if cryotherapy is not performed in Arm A and participants do not adhere to the strategy in Arm B. Per-protocol analysis will also be performed on only the participants who adhere to the specified procedures in Arms A and B, as secondary analysis. Participants without complete biopsy data will be censored at their last visit with a biopsy result (i.e., weeks 26, 78, 130).

Participants in Arm B may have biopsy done prior to week 26 based on the evaluation of baseline abnormal cervical cytology, whereas participants in Arm A will not have biopsies until week 26. Participants in Arm B diagnosed prior to their week 26 visit with CIN2+ that is cleared according to the biopsy at their week 26 will not be considered failures for the primary endpoint analysis. They are counted as meeting the primary endpoint only if CIN2+ is found at week 26 or later. Unplanned biopsies in Arm A that occur prior to the week 26 visit will not be considered for the primary endpoint.

The pathologic classification for the primary endpoint will be the determination by the local review at a DAIDS-assessed laboratory. Central review will be done for quality assurance.

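### SAP 3 replaces the protocol's Turnbull estimate with Kaplan-Meier without a stated reason or week scale, and lets a Pap smear extend CIN2+-free time

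*SAP*

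**What the plan says.** **Protocol.** Section 9.4 plans a "one-sided test using time-to-event methods that adjust for interval censored data at a type 1 error rate of 5"%. Section 9.6.1 names the estimator: "The protocol team plans to use the Turnbull estimation for the proportions of participants without CIN2+ diagnosis by the end of the study", with a generalized Greenwood variance and inverse-variance weighting over strata. It also gives the censoring rule: "Participants without complete biopsy data will be censored at their last visit with a biopsy result (i.e., weeks 26, 78, 130"). Section 9.6.2.1 carries the same method over to CIN3+.

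**SAP.** Section 3 counts weeks from randomization to the biopsy week, within 26 to 130, at which CIN2+ was first found. For women without CIN2+ it censors at the latest of "time of last biopsy or last colposcopy or last pap smear. The cumulative rate of CIN2+ will be estimated using Kaplan-Meier methods". Section 4.2.2 repeats the censoring rule for CIN3+ and names no estimator. Section 1 says that the SAP may be modified. No available passage gives a reason for this change.

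**Assessments.** Colposcopy with biopsy falls at weeks 26, 78 and 130; Pap smears are also taken at weeks 52 and 104 (Protocol 6.1). The window is ±6 weeks up to week 104 and ±12 weeks at week 130 (6.2.3). Version 1.0 took biopsies only where a lesion was seen. The letter of amendment that followed the March 2015 DSMB review changed this (item 2): "At least two cervical biopsies should be performed at the week 78 and week 130 visits", and "If no visible lesions are seen, then two random biopsies should be obtained".

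**The concern.** The endpoint is CIN2+ by biopsy, and disease can be found only at the biopsy visits. Two features of SAP 3 fit this badly.

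1. **Week scale.** Kaplan-Meier treats the detection week as the event time. If that is the scheduled visit, no harm follows. If it is the elapsed week, final visits spread from week 118 to week 142, and the estimate depends on where the curve is read. Read at week 130, it drops CIN2+ found at in-window visits in weeks 131–142. The SAP states neither the scale nor the reading point. An unstated choice in the primary estimate of an open-label trial could be settled after the data are seen. Double programming does not help, because it checks a definition and does not supply one.

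2. **Pap rule.** A woman with only a Pap smear at week 78 or 130 is counted as CIN2+-free there. A Pap smear cannot establish this; the sample size section itself reasons by "Assuming that the sensitivity of cervical cytology is approximately 80"%. Since the amendment, such a visit is an incomplete assessment and not a negative one.

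**Working it through.** **1. Design figure.** Inputs from Protocol 9.4: 20% vs 6%, one-sided 5%, 90% power, conservative Fisher-type calculation.

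- Uncorrected: n₀ = [1.645·√(2·0.13·0.87) + 1.282·√(0.20·0.80 + 0.06·0.94)]² / 0.14² = 96.9.
- Continuity-corrected: n = (96.9/4)·[1 + √(1 + 4/(96.9·0.14))]² = 110.8, so 111 per arm, as stated.
- With 20% loss: 111/0.80 = 138.75, so 139; the protocol enrols 140.

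The steps below use 140 per arm, 20% vs 6% and 20% loss. Visit timing, the spread of events over visits and the Pap-only share are assumptions; no document gives them.

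**2. Scheduled weeks, no missed colposcopy.** Let the events split equally over visits 26, 78 and 130 (6.67 points each in Arm B, 2 points each in Arm A). Kaplan-Meier in Arm B gives 1 − (1 − 0.0667)(1 − 0.0667/0.9333)(1 − 0.0667/0.8667) = 20%. Turnbull works on the same three intervals and agrees. A Pap smear at week 52 or 104 moves a censoring time into a gap with no event times, so no risk set changes. Simulation: Arm B 20.0–20.2%, Arm A 5.9–6.1%, power 96–97%; Turnbull 20.0–20.1% and 6.0–6.1%.

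**3. Actual weeks, read at week 130.** Let q be the chance of CIN2+ at the final visit given none before: 0.0667/0.8667 = 0.0769 in Arm B, 0.02/0.96 = 0.0208 in Arm A. Women still awaiting their final visit stay in the risk set. With F the fraction of final visits done by week 130, the rate is 1 − S₇₈·exp[q·ln(1 − F)], where S₇₈ is 0.8667 or 0.96. Early and late timing use a normal spread with SD 5 weeks, so F = Φ(±3/5).

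| Final visits | F | −ln(1−F) | Arm B | Arm A | Difference* | Simulated Arm B | Simulated power |
|---|---|---|---|---|---|---|---|
| symmetric | 0.50 | 0.693 | 17.8% | 5.4% | 12.5 | 17.7–18.2% | 89–92% |
| 3 weeks late | 0.274 | 0.321 | 15.4% | 4.6% | 10.8 | 15.1–15.8% | 89–90% |
| 3 weeks early | 0.726 | 1.294 | 21.5% | 6.6% | 15.0 | 21.6–21.9% | 88–91% |

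*From unrounded rates, in points.

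Separate runs gave 18.4%, 15.9% and 22.2% in Arm B, with power up to 93%. One-sided type I error, with the same timing in both arms, was 4.0–5.9%.

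**4. Actual weeks, read to week 142.** The last risk sets shrink to 3, 2 and 1 women, so a single late event moves the curve sharply. Expected survival is S₇₈·∏(1 − q/k) for k = 1 to n.

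- Equal split, Arm B: n = 140·0.80·0.8667 = 97, the product is 0.669, and the rate is 1 − 0.8667·0.669 = 42%.
- Events split 60/20/20: q = 0.04/0.84 = 0.0476, n = 94, and the rate is 34%.

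Simulations gave 33–35% (60/20/20 split, SD 16–19 points) and 38–43% (other onset models), with power 71–74%.

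**5. Pap rule on scheduled weeks.** Let m be the Pap-only share at weeks 78 and 130. A case first detectable at week 130 is lost with probability m; one first detectable at week 78 is lost only if both visits are Pap-only (m²). Loss = m·p₁₃₀ + m²·p₇₈, where p is the share of women whose CIN2+ is first detectable at that visit.

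| m | Arm B, equal split | Arm B, 60/20/20 |
|---|---|---|
| 10% | 20 − 0.67 − 0.07 = 19.3% | 20 − 0.40 − 0.04 = 19.6% |
| 20% | 20 − 1.33 − 0.27 = 18.4% | 20 − 0.80 − 0.16 = 19.0% |

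Simulation gave 19.2–19.7% and 18.1–19.1%, with power 94–96% and 93–95%. Arm A moves the same way (equal split: 5.8% and 5.5%). If the 80% of Pap-only cases with an abnormal smear were all worked up at that visit, Arm B would be 19.7–20.0%.

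**The case against.** The SAP's wording leans toward scheduled weeks. It uses week numbers as visit labels throughout, and where it wants elapsed time it names dates, as for study discontinuation in 4.2.6. On that reading the change of estimator has no numerical effect unless colposcopies are missed. This stands, and it makes scheduled weeks the likelier intent. It does not settle the matter, because SAP 3 also defines the event time as a count of weeks from randomization.

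The protocol's own rule is imperfect. Before the amendment a lesion-free colposcopy called for no biopsy, so censoring strictly at the last biopsy result would discard properly assessed women. This stands; a plain return to the protocol's wording is not the remedy. Protocol 9.6.1 also speaks only of the end of the study and does not say how week-130 visits within their window are treated, so that gap is not a SAP departure.

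The Pap effect is small and rests on an assumed share. Women with HSIL cytology and no visible lesion are also recalled: "the participant should return to the study clinic for repeat colposcopy and other diagnostics procedures". This stands too.

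Three stronger readings are tempting but unsupported:

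- **That SAP 4.2.2 also replaces Turnbull.** It repeats only the censoring rule.
- **That one dataset could give a difference anywhere from 11 to 15 points.** Those figures come from different assumed visit timings; they are neither two analyses of one dataset nor bounds.
- **That the change favours cryotherapy.** With equal visit timing in both arms, type I error stays near 5%, and the Pap rule lowers both rates and shrinks the difference.

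**Conclusion.** The concern holds as a departure that needs a stated reason and a definition that needs completing. It should be fixed, but it does not invalidate the analysis.

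The week scale is the main point. Scheduled weeks reproduce the design values. Actual weeks read at week 130 put Arm B at about 18% with symmetric final visits, 15–16% if they average 3 weeks late and about 22% if 3 weeks early, with power about 88–93% against a target of 90%. Actual weeks read to week 142 give an inflated, unstable estimate of about 33–43%, with power about 71–74%.

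The Pap rule is secondary: about 0.5–0.8 point in Arm B if 10% of week 78 and 130 visits are Pap-only and 1–2 points if 20% are, with power still above 90%.

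The departure itself is plain from the text. The sizes rest on assumed visit timing, event spread and Pap-only shares, so confidence in them is moderate.

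**What to change.** **SAP 3, estimator and time scale.** Either restore Turnbull with the protocol's variance, or assign results to scheduled visits 26, 78 and 130 before applying Kaplan-Meier. State that the rate is read at the week-130 visit, including its window to week 142. State to which scheduled visit an unscheduled work-up biopsy is assigned. Give the reason for any change from Protocol 9.6.1.

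**SAP 3 and 4.2.2, censoring.** Censor at the last visit with a biopsy result. Accept a lesion-free colposcopy instead only where the biopsy rule then in force called for no biopsy: week 26, and weeks 78 and 130 before the amendment. In the primary analysis, treat later week 78 or 130 visits without the required biopsies as not assessed, including those where biopsy was deferred for pregnancy (Protocol 7.4). Count lesion-free colposcopy at those visits only in a sensitivity analysis, and move the Pap smear to a sensitivity analysis as well.

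**Cost.** SAP wording and one reprogrammed derived variable; no new data. The price is slightly less follow-up from women whose last visit had only a Pap smear, or a colposcopy without the required biopsies.
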